6.4 DEVELOPMENT RATIONALE

RA101495 is being developed to treat patients with PNH. Based on PK and PD data generated to date, RA101495 has the potential to provide several advantages over the only currently approved therapy for PNH, eculizumab.

Daily administration of RA101495 is expected to result in near complete and sustained suppression of C5 for improved control of hemolysis. Continuous inhibition of hemolysis is important in the prevention of breakthrough hemolysis. Eculizumab at the approved dose of 900 mg biweekly has been associated with breakthrough hemolysis in some patients requiring dose increases beyond the approved dose described in the current product label [Hill, 2005]. Breakthrough hemolysis with eculizumab treatment typically occurs towards the end the biweekly infusion cycle and has been shown to be associated with sub-therapeutic eculizumab levels at those time points [Nakayama, 2016; Brodsky, 2014]. Daily dosing with RA101495 is designed to ensure that C5 is continuously inhibited and is therefore expected to eliminate end-of-cycle breakthrough episodes.

As a self-administered SC product, RA101495 has the potential to improve treatment satisfaction and improve dosing convenience for patients with PNH, and may enable a reduction in the cost of providing care. The current standard-of-care requires health professionals to administer eculizumab via a biweekly intravenous (IV) infusion. Published studies of patient preferences for SC versus IV therapy show a clear preference for SC administration, and SC administration has been shown to increase compliance, patient satisfaction and QOL, as well as reduce treatment costs, drug requirements, and the complications of intravenous access [Stoner, 2015; Besarab, 2002]. Phase 2 studies of RA101495 will include quantitative instruments for evaluating QOL.

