- Patients who have a known C5 mutation conferring resistance to eculizumab are included in this study. Eculizumab specifically binds to the terminal complement protein C5, inhibiting its cleavage into C5a and C5b by C5 convertases and thereby preventing the release of the inflammatory mediator C5a and the formation of the cytolytic pore C5b-9. Recently, two heterozygous mutations in the C5 gene localized to the C5 binding site have been identified which confer near-complete resistance to eculizumab [Nishimura, 2014]. One mutation (2654G→A) was identified in 11 Japanese patients with a poor response to eculizumab and the other was identified in an Argentinian patient of Asian ancestry (2653C→T). Both mutations result in nonsynonymous amino acid substitutions in the same critical arginine residue at position 885 of the C5 protein (Arg885His for 2654G→A; Arg885Cys for 2653C→T). These mutations markedly reduce the binding affinity of eculizumab for C5. Since RA101495 binds C5 at a site remote from the Arg885 residue, RA101495 has the potential that to retain efficacy in this subpopulation of refractory patients. In an *ex-vivo* study using C5 derived from one such patient, a related compound with similar potency, RA101348, completely inhibited hemolysis in an *in-vitro* lysis assay (Figure 13). Serum from the patient was acidified and mixed with RBCs in the presence (+) or absence (-) of RA101348 (Date on file, Ra Pharmaceuticals, Inc.; performed in the laboratory of [name], Osaka University).

Figure 13 **Inhibition of Hemolysis *in vitro* Lysis of PNH RBCs Without and With the Presence of RA101348 (identical peptide sequence to RA101495)**

Note: C5 Inhibitor =RA101348, a peptide inhibitor of Complement C5 with the same sequence as RA101495.

8.2 **STUDY PERIODS**

The total duration of study participation for all subjects will be up to 20 weeks, including a Screening Period of up to 8 weeks and a 12-week Treatment Period.

8.2.1 **SCREENING PERIOD**

The Screening Visit will occur at least 2 days, but no more than 56 days, before the first dose of RA101495 on Day 1.

8.2.2 **TREATMENT**

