9 SELECTION OF STUDY POPULATION

9.1 INCLUSION CRITERIA

To be eligible for this study, subjects must meet **ALL** of the following inclusion criteria:

1. Male or female ≥ 18 years
2. Completed informed consent procedures, including signing and dating the informed consent form (ICF).
3. Diagnosis of PNH by flow cytometry
4. Inadequate response to eculizumab defined as having received eculizumab for at least 6 months plus one or more of the following criteria:
 - A documented lactate dehydrogenase (LDH) level ≥ 1.5 x the ULN within 90 days prior to Screening
 - Presence of a known C5 mutation conferring resistance to eculizumab
5. Female subjects of child bearing potential must have a negative pregnancy test at Screening and within 24-hours prior to the first dose of RA101495
6. Sexually- active female subjects of child-bearing potential (i.e. women who are not post-menopausal or who have not had a bilateral oophorectomy, hysterectomy, or tubal ligation) and all male subjects (who have not been surgically sterilized by vasectomy) must agree to use effective contraception during the study. Effective contraception is defined as:
 - Hormonal contraception (e.g. oral contraceptive, transdermal contraceptive, contraceptive implant, or injectable hormonal contraceptive) for at least 3 months prior to study drug administration, throughout the study, and for 4 weeks after the last dose of study drug.
 - Double-barrier birth control (e.g. male condom, female condom, diaphragm sponge, or cervical cap together with spermicidal foam/gel/film/suppository) starting at the Screening Visit, throughout the study, and for 4 weeks after the last dose of study drug.
 - Intrauterine contraception/device starting at the Screening Visit, throughout the study, and for 4 weeks after the last dose of study drug.
 - Total abstinence from sexual intercourse for at least one complete menstrual cycle prior to the Screening Visit, throughout the study, and for 4 weeks after the last dose of study drug
 - Maintenance of a monogamous relationship with a male partner who has been surgically sterilized by vasectomy.

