- b. The Day 1 Visit should be scheduled to coincide with the next scheduled dose of eculizumab (i.e. 14 ± 2 after from the last eculizumab dose). Eculizumab should NOT be administered at the Day 1 Visit or at any time thereafter during the study.
- c. Height will be measured only at the Screening Visit.
- d. All subjects must have a negative throat swab for *Neisseria meningitidis* colonization for eligibility. All subjects must have documentation of prior *Neisseria meningitidis* vaccination (and booster if appropriate) prior to study entry.
- e. Including LDH for primary efficacy endpoint
- f. Coagulation tests should be performed, according to standard practice, on all subjects taking anticoagulant therapy.
- g. For all female subjects of childbearing potential, a negative serum pregnancy test must be documented at the Screening Visit and a negative urine pregnancy test must be documented at the Day 1 Visit prior to dosing. All other pregnancy tests will be urine.
- h. The injection site should be assessed at each clinic visit through Day 84 (End of Study).
- i. Blood samples for PK and PD and additional biomarker sampling at the following time points in relationship to the first dose of RA101495: pre-dose (within 1 hour before first dose administration) and at 1, 3, and 6 hours post-dose on Day 1. For subjects who have a dose increase to 0.3 mg/kg, samples for PK and PD should be collected at pre-dose Day 1 of the new dose, see footnote j. On clinic visit days PK and PD should be collected prior to administration of RA101495.
- j. Blood samples for PK of eculizumab should be collected at screening, Day 1, Day 15, Day 29, and Day 43 (2-week, 4-week, and 6-week) Visits. The sample should be collected prior to administration of RA101495.
- k. Blood sample for ADA on Day 1 must be obtained prior to dosing of RA101495.
- l. Blood sample for optional pharmacogenomic testing must be obtained on Day 1.
- m. On clinic visit days, the study drug RA101495 should be administered after blood samples for PK and PD are collected.

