3.1.3 Baseline Value and Change from Baseline (if applicable)

Baseline value is defined as the most recent non-missing value obtained immediately prior to administration of first dose (i.e., generally the study day 1 assessment which occurs pre-dose).

Change from baseline will be calculated by subtracting the baseline value from the post-dose assessment for each patient (i.e. post-dose – baseline). Percent change from baseline will be calculated as $100 \times \text{change score} / \text{baseline score}$.

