3.3.3 Secondary Efficacy Endpoints

Secondary efficacy variables include the change from baseline values at each of the following scheduled post-baseline assessment time-points:

- total hemoglobin,
- free hemoglobin,
- haptoglobin,
- reticulocytes
- hemoglobinuria.

Additionally, achieving an LDH < 1.5×ULN will be a secondary efficacy endpoint (i.e., a dichotomous endpoint) which will be assessed during the primary evaluation period and at each the scheduled post-baseline assessment time-points.

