3.9.2 Secondary Efficacy Endpoints Analysis

Secondary efficacy endpoints include the change from baseline values at each of the following scheduled post-baseline assessment time-points:

- total hemoglobin,
- free hemoglobin,
- haptoglobin,
- reticulocytes
- hemoglobinuria (note: hemoglobinuria will be assessed using a urine colorimetric scoring system).

The change from baseline for each of these endpoints will be assessed by a two-sided Wilcoxon signed-rank test. Additionally, the summary statistics will be presented for the values, change, and percent change from baseline scores.

Additionally, the secondary endpoint of an LDH score $< 1.5 \times \text{ULN}$ (i.e., a dichotomous endpoint) will be assessed at the primary evaluation period and the scheduled post-baseline assessment time-points by means of a one-sided exact McNemar's test.

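### Does the one-sided McNemar test of LDH <1.5×ULN fail because SAP 3.9.2 names neither the baseline half of the pair nor the Week 6–12 rule?

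*SAP*

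**What the plan says.** SAP 3.3.3 adds a dichotomous secondary endpoint, LDH <1.5×ULN, "which will be assessed during the primary evaluation period and at each the scheduled post-baseline assessment time-points". SAP 3.9.2 repeats that it "will be assessed at the primary evaluation period and the scheduled post-baseline assessment time-points by means of a one-sided exact" McNemar's test. Neither section names the status with which the post-baseline status is paired, the direction, or a significance level.

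Two definitions elsewhere in the SAP bear on this:
- SAP 3.1.3: "Baseline value is defined as the most recent non-missing value obtained immediately prior to administration of first dose". In general this is the pre-dose Day 1 sample.
- SAP 3.3.2 and 3.9.1: for the continuous primary endpoint, each patient's Week 6–12 value is the mean of the non-missing results at Weeks 6, 8, 10 and 12. SAP 3.9.1 also summarises that patient mean itself.

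On status at entry, Protocol 9.1 asks for at least six months of eculizumab plus either one LDH at or above 1.5 times "ULN within 90 days prior to Screening" or "Presence of a known C5 mutation conferring resistance to eculizumab". Protocol 8.2.1 adds: "The Screening Visit will occur at least 2 days, but no more than 56 days, before the first dose". No LDH threshold applies at Screening or on Day 1. On timing, the SAP schedule says "The Day 1 Visit should be scheduled to coincide with the next scheduled dose of eculizumab", and Protocol 6.4 notes that "Breakthrough hemolysis with eculizumab treatment typically occurs towards the end the biweekly infusion cycle".

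**The concern.** McNemar's test compares two statuses in the same subject and uses only the subjects whose status differs. Taken alone, SAP 3.9.2 gives one half of the pair. If the other half is baseline, eligibility does not fix it. The qualifying LDH can be up to 90 + 56 = 146 days old at first dose, and a subject who enters through a C5 mutation needs no raised LDH. Anyone already below 1.5×ULN at baseline who stays there drops out of the test.

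The second half also looks open for Weeks 6–12. A subject could be classed by the mean, by every visit or by any visit, and these rules can disagree.

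LDH <1.5×ULN is the criterion for adequate response in SAP 2.2, and McNemar is the only test planned for it. With 6–8 subjects, classing one or two differently changes the p-value materially. Shift tables are planned for FACIT-Fatigue and EQ-5D items, but none is named for LDH status.

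**Working it through.** **Inputs.** Planned n of 6–8 (SAP 2.2.1); SD 443 U/L and correlation 0.8 (SAP 3.11); the test from SAP 3.9.2. The plan gives no sizing figure and no significance level for the McNemar test. A one-sided 5% level is assumed below for illustration only.

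**The plan's own figure.** SE of the mean LDH change = 443 × √(2 × (1 − 0.8)) / √6 = 280.18 / 2.449 = 114.4 U/L. This matches the stated 114 U/L. It concerns the continuous endpoint, not this test.

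**Effect of baseline status.** Let b subjects move from ≥1.5 to <1.5×ULN and c move the other way. The exact one-sided p is P(X ≥ b) for X ~ Binomial(b + c, 0.5). With c = 0 it is 0.5^b.

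| Already below at baseline, staying below | Best p, n = 6 | Best p, n = 8 |
|---|---|---|
| 0 | 0.0156 | 0.0039 |
| 1 | 0.0313 | 0.0078 |
| 2 | 0.0625 | 0.0156 |
| 3 | 0.125 | 0.0313 |
| 4 | 0.25 | 0.0625 |

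At the assumed 5% level, two such subjects at n = 6, or four at n = 8, put significance out of reach. The documents do not say how many subjects will be below. If each is below with an assumed chance q, independently:

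- n = 6: P(≥2) = 1 − (1 − q)^6 − 6q(1 − q)^5 = 3%, 11%, 34%, 58% for q = 5%, 10%, 20%, 30%.
- n = 8: P(≥4) = 0.04%, 0.5%, 5.6%, 19% for the same q.

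**Can q be taken from the plan's SD and correlation?** No. Given a qualifying value x above the threshold and a population mean m above it, Day 1 LDH would have mean m + 0.8(x − m) and SD 443 × √(1 − 0.8²) = 265.8. The documents do not give m. With x = 100 U/L, assuming m = 400 gives Φ(−160/265.8) = 27%, and assuming m = 800 gives Φ(−240/265.8) = 18%. The 0.8 also refers to baseline against post-baseline, not to a historical value against Day 1.

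**Effect of the Week 6–12 rule.** Values of 1.2, 1.3, 1.3 and 1.9 ×ULN have mean 5.7/4 = 1.425, which meets the criterion, while an every-visit rule does not. In a simulation with an assumed true level of 1.4×ULN and within-subject CV of 15% (log-normal), the chance of being called a responder is 0.83 by the mean, 0.25 by all four visits and 0.99 by any visit. The choice of rule therefore matters. The question is whether the text leaves a real choice.

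**Reading the sections together.** The study has one arm, so the pair can only be within subject over time. The SAP has one baseline definition, and the tests of LDH, the other secondary endpoints and PD in SAP 3.9.1–3.9.3 are all of change from it. For Weeks 6–12 the SAP defines one value per patient, the mean of non-missing results. SAP 3.9.2 speaks of status at that period, alongside the individual time-points, which treats it as a single occasion. No section suggests an every-visit or any-visit rule.

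**What a reader can recover.** If 6 of 6 are below on treatment and 2 of 6 were below at baseline, nobody can have reversed (c = 0), so b = 6 − 2 = 4 and p = 0.5^4 = 0.0625. The two margins fix the number of changes. Where reversals occur, the margins give only b − c. But SAP 3.1.2 puts all study data in listings, and the post-lock list includes LDH history, efficacy assessments and clinical chemistry. With 6–8 subjects the changes can be counted from these. The analyst must in any case form the 2×2 table to run the test.

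**The case for a change.** The strongest case for a change is that the SAP names the reference for its other tests, either change from baseline or the neutral score of 3 for treatment satisfaction, and leaves it unstated here. The protocol cannot fill the gap: it does not list this endpoint, and its section 13.3.5 plans no formal comparisons. The mean in SAP 3.3.2 is written for the continuous endpoint only. One sentence and one cross-table would settle everything.

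Part of this stands. The link to SAP 3.1.3 and 3.3.2 is unwritten, the p-values above are right, and a baseline-by-post-baseline table would help a reader. Three things limit its weight.

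- Subjects below threshold at baseline do not invalidate McNemar's test. They leave fewer informative pairs, which is correct, because a subject who starts and stays below shows no change. The setting also argues against many low baselines: the protocol's rationale describes the qualifying C5 mutations as making eculizumab almost ineffective, and Day 1 falls at the end of the dosing cycle, when breakthrough is typical.
- No decision rests on p <0.05. Failing to reach a threshold that the plan never sets has no planned consequence.
- The text reviewed may not be the text in force at lock. The post-lock document refers to SAP Version 3.0 of 22 March 2018. It lists total bilirubin tables without the mark for new or modified items, yet the SAP's own table list has none. Version 3.0 or the separate table shells may already state the pair and the rule, which cannot be checked here.

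**Conclusion.** No change follows. This is a gap in wording that an analyst fills in one sensible way: status at the SAP 3.1.3 baseline against status at each visit and, for Weeks 6–12, against the status of the SAP 3.3.2 mean, with the one-sided alternative that more subjects are below 1.5×ULN on treatment. Read so, the test is valid and its p-value is exact.

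The sensitivity is real but comes from the sample size: with complete response at n = 6, p runs from 0.0156 with nobody below at baseline to 0.0625 with two. That is the test reporting fewer changes, not an error. A cross-table, a subset confidence interval or extra listing columns would aid presentation but would correct no wrong result in a fully listed study of 6–8 subjects.

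The conclusion rests on three assumptions: that analysts follow the natural reading, that no success criterion for this endpoint exists outside the documents, and that the listings show LDH and its ULN for each subject. The primary LDH endpoint is not affected.

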3.9.3 Pharmacodynamic Endpoints Analysis

The pharmacodynamic endpoints include:

- Changes from baseline CH_{50}
- Changes from baseline in sRBC lysis for the classical complement pathway

- Changes from baseline in Wieslab ELISA for alternative complement pathway
- Changes from baseline in C5 concentration levels.

The change from baseline for each of these endpoints will be assessed by a two-sided Wilcoxon signed-rank test. Additionally the summary statistics will be presented for the values, change, and percent change from baseline scores.

3.9.4 Pharmacokinetic Endpoints Analysis

The following pharmacokinetic endpoints will be summarized using descriptive statistics:

- Plasma concentrations of RA101495 and its major metabolites
 - Maximum plasma concentration (C_{\max})
 - Time corresponding to C_{\max} (t_{\max})
 - Area under the drug concentration-time curves (AUC_{0-t})
- Plasma concentrations of eculizumab.

3.9.5 Exploratory Endpoints Analysis

3.9.5.1 EORTC QLQ-C30

Summary statistics for each scales/items scores (Section 3.3.6.1) will be presented as well as the corresponding change from baseline scores for each scheduled assessment time-point.

Global health status

- Global health status/QoL

Functional scales

- Physical functioning
- Role functioning
- Emotional functioning
- Cognitive functioning
- Social functioning

Symptom scales/items

- Fatigue
- Nausea and vomiting
- Pain
- Dyspnoea
- Insomnia
- Appetite loss

- Constipation
- Diarrhoea
- Financial difficulties.

The change from baseline for the EORTC QLQ-C30 scales will be assessed by a two-sided Wilcoxon signed-rank test.

3.9.5.2 FACIT-Fatigue

The overall FACIT-Fatigue score and the individual 13 item scores (Section 3.3.6.2) will be summarized as well as the corresponding change from baseline scores for each scheduled assessment time-point. Shift tables displaying the individual item values from baseline to each post-baseline visit will also be presented.

The change from baseline for the FACIT-Fatigue overall and individual item scores will be assessed by a two-sided Wilcoxon signed-rank test.

3.9.5.3 EQ-5D

The five EQ-5D scale scores (score values range 1 – 3) and the VAS score (Section 3.3.6.3) will be summarized as well as the corresponding change from baseline scores for each scheduled assessment time-point. Shift tables displaying the individual dimension values from baseline to each post-baseline visit will also be presented.

The change from baseline for the EQ-5D VAS score will be assessed by a two-sided Wilcoxon signed-rank test. For this change from baseline analysis the item response categories (e.g., 1, 2, and 3) will be summarized as a continuous variable.

3.9.5.4 Treatment Satisfaction Questionnaires

For both treatment satisfaction questions (Section 3.3.6.4) the number and percentage for each response category will be summarized.

Both treatment satisfaction will be assessed by a two-sided Wilcoxon signed-rank test testing against a score of neutral. This is equivalent to subtracting 3 from each of the scores and testing against a score of 0 (i.e., the default for a Wilcoxon signed-rank test).

3.10 Interim Analysis

During this open-label study, the Sponsor will review safety and efficacy data as it becomes available during the Treatment Period. Following completion of the 12-week Treatment Period, data will be cleaned and locked at the individual subject level, and will be available for final analysis by the Sponsor on a rolling basis.

3.11 Sample Size Considerations

A sample size of 6 subjects will yield a standard error of approximately 114 U/L for an LDH mean change-from-baseline estimate. This assumes a standard deviation of 443 U/L for the baseline and post-baseline endpoints, and a within-subject correlation estimate of 0.8.

3.12 Replacement of Subjects

Enrolled subjects who prematurely discontinue study treatment for any reason prior to the Day 84 Visit may be replaced, at the discretion of the Sponsor.

4 References

EuroQol Group. EuroQol-a new facility for the measurement of health-related quality of life. *Health Policy* 1990; 16:199-208.

5 List of Tables, Figures, and Listings

Table shells will be provided in a separate document.

Table Number	Table Title
14.1.1	Patient Disposition
14.1.2.1	Medical History; Safety Population
14.1.2.2	PNH Disease History; Safety Population
14.1.2.3	PNH Treatment History; Safety Population
14.1.3.1	Prior Medications; Safety Population
14.1.3.2	Concomitant Medications; Safety Population
14.1.4	Exposure to Study Treatment; Safety Population
14.1.5.1	Demographics; Safety Population
14.1.5.2	Demographics; Efficacy Evaluable Population
14.1.5.3	Demographics; Per Protocol Population
14.1.5.4	Demographics; Pharmacodynamic Population
14.2.1.1	Summary of LDH Values; Safety Population
14.2.1.2	Summary of LDH Values; Efficacy Evaluable Population
14.2.1.3	Summary of LDH Values; Per Protocol Population
14.2.1.4	Summary of LDH Values; Pharmacodynamic Population
14.2.2.1	Summary of Total Hemoglobin Values; Safety Population
14.2.2.2	Summary of Total Hemoglobin Values; Efficacy Evaluable Population
14.2.2.3	Summary of Total Hemoglobin Values; Per Protocol Population
14.2.2.4	Summary of Total Hemoglobin Values; Pharmacodynamic Population
14.2.3.1	Summary of Free Hemoglobin Values; Safety Population
14.2.3.2	Summary of Free Hemoglobin Values; Efficacy Evaluable Population
14.2.3.3	Summary of Free Hemoglobin Values; Per Protocol Population

Table Number	Table Title
14.2.3.4	Summary of Free Hemoglobin Values; Pharmacodynamic Population
14.2.4.1	Summary of Haptoglobin Values; Safety Population
14.2.4.2	Summary of Haptoglobin Values; Efficacy Evaluable Population
14.2.4.3	Summary of Haptoglobin Values; Per Protocol Population
14.2.4.4	Summary of Haptoglobin Values; Pharmacodynamic Population
14.2.5.1	Summary of Reticulocyte Values; Safety Population
14.2.5.2	Summary of Reticulocyte Values; Efficacy Evaluable Population
14.2.5.3	Summary of Reticulocyte Values; Per Protocol Population
14.2.5.4	Summary of Reticulocyte Values; Pharmacodynamic Population
14.2.6.1	Summary of Hemoglobinuria Values; Safety Population
14.2.6.2	Summary of Hemoglobinuria Values; Efficacy Evaluable Population
14.2.6.3	Summary of Hemoglobinuria Values; Per Protocol Population
14.2.6.4	Summary of Hemoglobinuria Values; Pharmacodynamic Population
14.2.7.1	Summary of CH ₅₀ Values; Pharmacodynamic Population
14.2.8.1	Summary of sRBC Values; Pharmacodynamic Population
14.2.9.1	Summary of Wieslab ELISA Values; Pharmacodynamic Population
14.2.10.1	Summary of C5 Concentration Values; Pharmacodynamic Population
14.2.11.1	Plasma RA101495 Concentrations; PK Population
14.2.11.2	Plasma Eculizumab Concentrations; PK Population
14.2.11.3	Plasma RA101495 PK Parameters; PK Population
14.2.12.1	Summary of EORTC QLQ-C30; Safety Population
14.2.12.2	Summary of EORTC QLQ-C30; Per Protocol Population

Table Number	Table Title
14.2.13.1	Summary of FACIT-Fatigue: Overall Score; Safety Population
14.2.13.2	Summary of FACIT-Fatigue: Overall Score; Per Protocol Population
14.2.13.3	Summary of FACIT-Fatigue: Items; Safety Population
14.2.13.4	Summary of FACIT-Fatigue: Items; Per Protocol Population
14.2.13.5	Summary of FACIT-Fatigue: Items Shift Table; Safety Population
14.2.13.6	Summary of FACIT-Fatigue: Items Shift Table; Per Protocol Population
14.2.14.1	Summary of EQ-5D: Health State VAS Score; Safety Population
14.2.14.2	Summary of EQ-5D: Health State VAS Score; Per Protocol Population
14.2.14.3	Summary of EQ-5D: Individual Dimensions; Safety Population
14.2.14.4	Summary of EQ-5D: Individual Dimensions; Per Protocol Population
14.2.14.5	Summary of EQ-5D: Individual Dimensions Shift Table; Safety Population
14.2.14.6	Summary of EQ-5D: Individual Dimensions Shift Table; Per Protocol Population
14.2.15.1	Summary of Treatment Satisfaction; Safety Population
14.2.15.2	Summary of Treatment Satisfaction; Per Protocol Population
14.3.1.1	Overall summary of Treatment Emergent Adverse Events; Safety Population
14.3.1.2.1	Incidence of Treatment Emergent Adverse Events by System Organ Class and Preferred Term; Safety Population
14.3.1.2.2	Incidence of Treatment Emergent Adverse Events by System Organ Class, Preferred Term, and Maximum Severity; Safety Population
14.3.1.2.3	Incidence of Treatment Emergent Adverse Events by System Organ Class, Preferred Term, and Relationship to Study Drug; Safety Population

Table Number	Table Title
14.3.1.2.4	Incidence of Treatment Emergent Adverse Events Leading to Discontinuation of Study Drug by System Organ Class and Preferred Term; Safety Population
14.3.1.3	Listing of Serious Adverse Events by System Organ Class and Preferred Term; Safety Population
14.3.1.4	Incidence of Thrombotic Treatment Emergent Adverse Events by System Organ Class, and Preferred Term; Safety Population
14.3.1.5	Summary of Injection Site Reaction Assessments; Safety Population
14.3.2.1	Summary of Hematology Values; Safety Population
14.3.2.2	Summary of Clinical Chemistry Values; Safety Population
14.3.2.3	Summary of Coagulation Values; Safety Population
14.3.2.4	Summary of C-Reactive Protein and Creatine Phosphokinase Values; Safety Population
14.3.2.5	Summary of Liver Function Test Values – NCI CTCAE Grading; Safety Population
14.3.2.6	Summary of Pancreatic Enzyme Test Values – NCI CTCAE Grading; Safety Population
14.3.2.7	Summary Anti-Drug Antibodies; Safety Population
14.3.3	Summary of PNH Clone Size Values Safety Population
14.3.4	Summary of Vital Signs; Safety Population
14.3.5.1	Summary of ECG Interpretation; Safety Population
14.3.5.2	Summary of ECG Values; Safety Population

Figure Number	Figure Title
14.2.1.1	Mean LDH Values Over Time; Safety Population
14.2.1.2	Mean LDH Values Over Time; Efficacy Evaluable Population
14.2.1.3	Mean LDH Values Over Time; Per Protocol Population
14.2.1.4	Mean LDH Values Over Time; Pharmacodynamic Population
14.2.2.1	Mean Total Hemoglobin Values Over Time; Safety Population
14.2.2.2	Mean Total Hemoglobin Values Over Time; Efficacy Evaluable Population
14.2.2.3	Mean Total Hemoglobin Values Over Time; Per Protocol Population
14.2.2.4	Mean Total Hemoglobin Values Over Time; Pharmacodynamic Population
14.2.3.1	Mean Free Hemoglobin Values Over Time; Safety Population
14.2.3.2	Mean Free Hemoglobin Values Over Time; Efficacy Evaluable Population
14.2.3.3	Mean Free Hemoglobin Values Over Time; Per Protocol Population
14.2.3.4	Mean Free Hemoglobin Values Over Time; Pharmacodynamic Population
14.2.4.1	Mean Haptoglobin Values Over Time; Safety Population
14.2.4.2	Mean Haptoglobin Values Over Time; Efficacy Evaluable Population
14.2.4.3	Mean Haptoglobin Values Over Time; Per Protocol Population
14.2.4.4	Mean Haptoglobin Values Over Time; Pharmacodynamic Population
14.2.5.1	Mean Reticulocyte Values Over Time; Safety Population
14.2.5.2	Mean Reticulocyte Values Over Time; Efficacy Evaluable Population
14.2.5.3	Mean Reticulocyte Values Over Time; Per Protocol Population

Figure Number	Figure Title
14.2.5.4	Mean Reticulocyte Values Over Time; Pharmacodynamic Population
14.2.6.1	Mean Hemogloubinuria Values Over Time; Safety Population
14.2.6.2	Mean Hemogloubinuria Values Over Time; Efficacy Evaluable Population
14.2.6.3	Mean Hemogloubinuria Values Over Time; Per Protocol Population
14.2.6.4	Mean Hemogloubinuria Values Over Time; Pharmacodynamic Population
14.2.7.1	Mean CH ₅₀ Values Over Time – Semi-Log Scale; Pharmacodynamic Population
14.2.7.2	Mean CH ₅₀ Values Over Time – Linear Scale; Pharmacodynamic Population
14.2.8	Mean sRBC Values Over Time; Pharmacodynamic Population
14.2.9	Mean Wieslab ELISA Values Over Time; Pharmacodynamic Population
14.2.10	Mean C5 Concentration Values Over Time; Pharmacodynamic Population
14.2.11	Mean Plasma RA101495 Concentrations Over Time; PK Population
14.2.12	Mean Plasma Eculizumab Concentrations Over Time; PK Population

Listing Number	Listing Title
16.2.1	Patient Disposition; Safety Population
16.2.2.1	Medical History; Safety Population
16.2.2.2	PNH Disease History; Safety Population
16.2.2.3	PNH Treatment History; Safety Population
16.2.2.4	Neisseria meningitidis Testing
16.2.3.1	Prior Medications; Safety Population
16.2.3.2	Concomitant Medications; Safety Population
16.2.4.1	Treatment Compliance; Safety Population
16.2.4.2	Exposure to Study Treatment; Safety Population
16.2.5	Demographics; Safety Population
16.2.6	Pharmacodynamic Endpoints
16.2.7.1	Plasma Pharmacokinetic Sample Collection Times and RA101495 Concentrations
16.2.7.2	Individual Plasma RA101495 PK Parameters
16.2.8.1	EORTC QLQ-C30; Safety Population
16.2.8.2	FACIT-Fatigue; Safety Population
16.2.8.3	EQ-5D; Safety Population
16.2.8.4	Treatment Satisfaction; Safety Population
16.2.9	Adverse Events
16.2.10	Injection Site Reactions
16.2.11.1	Hematology
16.2.11.2	Clinical Chemistry
16.2.11.3	Coagulation, C-Reactive Protein, and Creatine Phosphokinase
16.2.11.4	Urinalysis
